5.1.1.1 Dose-Limiting Toxicity Assessment Window

The DLT assessment window is the 28 days in the first cycle (Days 1-28). Any patient considered to be non-evaluable for DLT as defined below was to be replaced by an additional patient at that same dose level.

5.1.1.2 Definition of DLT Evaluable Patients

A patient will be DLT evaluable if the patient:

- Has not received any preventive treatment during the DLT period; AND
- Has completed the first 28-day treatment cycle with complete safety evaluations and has received at least 75% of the assigned surufatinib dose;

OR

- Has a confirmed DLT during the first 28-day treatment cycle.

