5 INVESTIGATIONAL PLAN

5.1 Description of the Study

This is an open-label trial of surufatinib taken orally once daily (QD), and it consists of two phases: a dose escalation phase in patients with advanced solid tumors of any type, and a dose expansion phase in patients with advanced BTC (Arm A), advanced pNETs (Arm B), advanced epNETs (Arm C), or STSs (Arm D). The two phases will be conducted as described below.

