5.1.1 Dose Escalation Phase

A 3+3 design will be used for this phase of the study. As of Amendment 7, a total of 35 evaluable patients have been enrolled in the dose escalation phase and the MTD/RP2D has been declared at 300 mg QD.

The trial was to evaluate 5 dose levels of surufatinib 50 mg, 100 mg, 200 mg, 300 mg and 400 mg on a QD dosing schedule.

A minimum of 3 patients were to be enrolled and observed for toxicity at each dose level. If the 3 patients initially enrolled in a dose cohort completed the DLT assessment window (Cycle 1, Days 1-28) without experiencing a DLT, another 3 patients were to be enrolled at the next higher dose level. If 1 of the initial 3 patients enrolled at any dose level experienced a DLT during the DLT assessment window, additional patients were to be enrolled at that dose level for a minimum of 6 evaluable patients for the DLT evaluation. If 1 DLT was observed in 1 of the 6 evaluable patients at this dose level, dose escalation was to proceed to the next pre-defined dose level. If 2 or more DLTs were observed in the 6 evaluable patients at a given dose level, the dose escalation was to be halted. If this dose level was $\geq 50\%$ higher than the previous dose level, an intermediate dose level was to be evaluated for toxicity in the same manner as described above. If the dose level was $< 50\%$ higher than the previous dose level, additional patients were to be enrolled at the previous dose level, if necessary, to form a dose cohort of minimum 6 evaluable patients. The MTD is the highest dose reached with no more than 1 DLT among 6 evaluable patients.

Pharmacokinetic samples will be collected as specified in [Table 12](#).

Safety monitoring and evaluation for dose escalation will be carried out by the Safety Review Committee (SRC) upon completion of the DLT observation period of each cohort. Dose escalation decisions are based on safety and PK data from this ongoing trial, as well as consideration of safety and PK data at comparable drug exposures from patients in previously conducted clinical trials in China.

If a patient meets any DLT non-evaluable criteria during the DLT assessment period, the patient will be replaced.

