5.1.1.3 Definition of a Dose-Limiting Toxicity (DLT)

All AEs, including DLTs, are to be graded according to the NCI CTCAE, v. 4.03. A DLT is defined as one of the following toxicities occurring during the DLT assessment window (Cycle 1, Days 1-28) and determined by the investigator to have a reasonable possibility of being related to surufatinib.

- Any Grade 4 non-hematological toxicity;
- Any Grade 3 non-hematological toxicity except for nausea/vomiting, diarrhea, constipation, electrolyte imbalances, or transient hypertension downgraded within 3 days with appropriate supportive treatment;
- Grade 4 neutropenia lasting >7 days;
- Grade 3 febrile neutropenia (absolute neutrophil count $<1.0 \times 10^9/L$ with a single temperature of $>38.3^{\circ}\text{C}$ or a sustained temperature of $\geq 38^{\circ}\text{C}$ for more than one hour);
- Grade 4 thrombocytopenia or \geq Grade 3 thrombocytopenia associated with tendency to bleed;
- Dose interruption or delay for >14 days due to toxicity;
- Any life-threatening complication or abnormality not covered in the NCI CTCAE v. 4.03.

In the absence of clinical abnormality, repeat laboratory testing will be conducted to confirm significant laboratory findings prior to designation as a DLT.

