Grade 2: 2+ or 3+ proteinuria; urinary protein 1.0 - 2.0 g (excluding 2.0 g)/24 hours	None.	Provide supportive treatment and increase the frequency of urine monitor to once a week; consult nephrologist if necessary.
Grade 2: Proteinuria \geq 2+; urinary protein 2.0 - 3.5 g (excluding 3.5 g)/24 hours	Hold surufatinib treatment and resume treatment at the same dose level if proteinuria resolves to \leq Grade 1 within 21 days	Provide supportive treatment and increase the frequency of urine monitor to once a week; consult nephrologist if necessary.
Grade 3: Urinary protein \geq 3.5 g/24 hours	Hold surufatinib. If test results resolves to \leq Grade 1 within 21 days, resume at a lower dose.	Provide supportive treatment and increase the frequency of urine monitor to once or twice a week; consult nephrologist if necessary.

^a If urine dipstick reveals proteinuria 2+, 24-hour urine collection should be performed for determination of total protein within one week. The CTCAE grade recorded for proteinuria should be determined by the 24-hour urine collection, however the start date of the AE will be recorded as the first instant of proteinuria (i.e. urine dipstick). If surufatinib dose has been reduced to 200mg QD and a further dose reduction is required for recurrent proteinuria, keep the same daily dose of 200 mg QD of surufatinib for 3 consecutive weeks followed by 1-week drug holiday and repeat for each treatment cycle, (i.e. 3 weeks on and 1 week off; every 4 weeks constitutes a treatment cycle). If proteinuria cannot resolve to \leq Grade 1 after a dose interruption of 21 days, continuation/resumption of surufatinib treatment should be discussed with the medical monitor. Surufatinib treatment should be discontinued if a patient develops nephrotic syndrome.

Table 9 Dose Modification for Liver Function Impairment

Grade and Definitions	Dose Adjustment	Suggested Actions
Grade 1: ALT >1-3 \times ULN or AST >1-3 \times ULN	None.	Follow up per planned schedule. Check total bilirubin. ^a
Grade 2: ALT >3-5 \times ULN or AST >3-5 \times ULN	Maintain the original dose, provide supportive care of complications of liver impairment, observation for 1 week, If the ALT and AST is	Check total bilirubin. ^a Provide supportive care and increase the frequency of liver function monitor to 1-2 times a week.

Table 9 Dose Modification for Liver Function Impairment

Grade and Definitions	Dose Adjustment	Suggested Actions

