6.3. DOSING LIMITING TOXICITY (DLT) EVALUABLE SET

The DLT set comprises all SAS patients who are evaluable for DLT assessment. DLT evaluable patients can be identified via answers to the question “DLT evaluable patients” on CRF “DLT Assessment” page.

DLT set (and summaries of DLTs) only applies to dose escalation phase patients.

A DLT evaluable patient has to meet the following criteria, which will not be confirmed via programming:

- Has not received any preventive treatment during the DLT period; AND
- Has completed the first 28-day treatment cycle with complete safety evaluations and has received at least 75% of the assigned surufatinib dose; OR
- Has a confirmed DLT during the first 28-day treatment cycle.

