17.1.6. Dose Limiting Toxicity (DLT)

A detailed definition of DLT can be found in Protocol Section 4.1.2. On the CRF, DLT will be identified among all AEs using question “Is it DLT?”, and details will be captured on CRF page “DLT Assessment”. Incidence of DLTs by SOC and PT will be summarized for DLT set. Time between date of first dose of study medication and DLT event onset will be presented for DLT evaluable set.

All relevant information of DLT assessment will be listed for DLT evaluable set by dose cohort and by patient.

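### Escalation patients held 8 to 14 days in Cycle 1 for toxicity that meets no DLT criterion are replaced, so the DLT summary can omit patients because they did not tolerate the dose

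*Protocol*

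**What the plan says.** The escalation primary endpoint is the incidence of DLTs in each cohort (Protocol 4.1.2). Four rules determine who enters it.

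- **Evaluability.** Protocol 5.1.1.2, repeated in SAP 6.3, bars preventive treatment and gives two routes. One is exposure: "Has completed the first 28-day treatment cycle with complete safety evaluations and has received at least 75% of the assigned surufatinib dose". The other is a confirmed DLT in Cycle 1.
- **Interruption as a DLT.** Protocol 5.1.1.3 lists "Dose interruption or delay for >14 days due to toxicity"; Protocol 4.1.2 uses the same 14-day limit.
- **Replacement.** Protocol 5.1.1 states: "If a patient meets any DLT non-evaluable criteria during the DLT assessment period, the patient will be replaced". Section 5.1.1.1 repeats this, and neither makes an exception when the shortfall was caused by the drug.
- **Analysis.** SAP 6.3: "The DLT set comprises all SAS patients who are evaluable for DLT assessment". SAP 17.1.6: "Incidence of DLTs by SOC and PT will be summarized for DLT set". Protocol 10.4 agrees.

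The dose-modification text in Protocol 7.2 allows treatment delays of up to 21 days and calls for holds for some events that are not in themselves DLTs. For proteinuria of 2.0 to below 3.5 g per 24 hours, Table 8 reads "Hold surufatinib treatment and resume treatment at the same dose level if proteinuria resolves to" Grade 1 or lower within 21 days. Table 9 interrupts for Grade 2 ALT/AST that keeps rising significantly. Table 10 holds for Grade 2 hemorrhage. Table 6 covers Grade 3 hematologic toxicity, some of which (neutropenia without fever, thrombocytopenia without bleeding) is not a DLT.

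**The concern.** The 75% rule and the 14-day rule do not meet. Between them lies a group of patients who lose a substantial part of Cycle 1 to drug toxicity but have no listed DLT. The evaluability rule treats them like patients who missed doses for unrelated reasons: they leave the denominator and someone else takes their place.

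That makes the exclusion depend on the outcome. The phase is meant to evaluate safety and tolerability and to find the MTD/RP2D, yet the planned DLT table describes only patients who took at least 75% of the dose or had a listed DLT. The MTD rule allows no more than 1 DLT among 6, so a single patient can matter, and all four expansion arms use the resulting 300 mg dose.

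**Working it through.** **No stated figure to reproduce.** The documents give no operating characteristics for the 3+3 phase.

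**Step 1: the width of the gap.** The window is 28 days (Protocol 5.1.1.1) with one dose per day (5.1), so 28 planned doses. The minimum is 0.75 × 28 = 21 doses. Share taken = (28 − missed)/28.

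| Full doses missed | Share taken | Evaluable on exposure | Interruption DLT |
|---|---|---|---|
| 7 | 21/28 = 75.0% | yes | no |
| 8 | 20/28 = 71.4% | no | no |
| 14 | 14/28 = 50.0% | no | no |
| 15, consecutive | 13/28 = 46.4% | no, but enters through the DLT route | yes |

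The gap is 8 to 14 missed full doses. This counts doses at the assigned level; dose reductions also use up part of the 75%. If the 14-day rule means one continuous interruption, scattered missed days could carry the gap above 14.

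**Step 2: effect on one cohort.** Take seven treated patients: one with a DLT, five without, one in the gap.

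- Gap patient replaced, as written: 1/6 = 16.7%.
- Kept and counted as not tolerating the dose: 2/7 = 28.6%.
- Kept as evaluable without a DLT: 1/7 = 14.3%.

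**Step 3: effect on the 3+3 rule.** Let p be the probability of a DLT and q the probability of falling in the gap, the two being mutually exclusive and patients independent. Both are assumptions; the documents give neither. The rate r entering the count is:

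- replaced: r = p/(1 − q)
- counted as not tolerating: r = p + q
- kept without a DLT: r = p

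A level is cleared on 0/3, or on 1/3 followed by 0/3: P = (1 − r)³ + 3r(1 − r)² × (1 − r)³.

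At p = 20%:

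| q | Replaced: r, P(clear) | Counted: r, P(clear) | Kept without DLT: r, P(clear) |
|---|---|---|---|
| 5% | 21.1%, 68.6% | 25%, 60.0% | 20%, 70.9% |
| 10% | 22.2%, 66.0% | 30%, 49.4% | 20%, 70.9% |
| 15% | 23.5%, 63.2% | 35%, 39.6% | 20%, 70.9% |
| 20% | 25.0%, 60.0% | 40%, 30.9% | 20%, 70.9% |

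Over p from 5% to 20% and q of 5%, 10% or 20%, replacement raises the chance of clearing a level, relative to counting, by between 6.5 points (p = q = 5%: 97.1% against 90.6%) and 36.8 points (p = 10%, q = 20%: 86.2% against 49.4%).

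**Step 4: direction.** p/(1 − q) is below p + q whenever q(1 − p − q) > 0, that is, whenever some patients have neither outcome. It is above p for any q > 0. The sign of the difference therefore depends on the comparison.

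**The case against.** The best counter-arguments, and what stands of each:

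- **Most toxicity holds are already DLTs.** A reader might infer that every patient missing 8 to 14 doses for toxicity drops out. That is not so. All related Grade 4 and most related Grade 3 non-hematologic toxicity is a DLT, so those patients stay evaluable. Not all Grade 2 events are held either: proteinuria of 1.0 to below 2.0 g needs no dose change, and Grade 2 ALT/AST is observed for a week at the original dose first. This stands and narrows the point to the remaining events.
- **Replacement does not always understate toxicity.** Under the protocol's own DLT definition it gives p/(1 − q), above p, and is the more conservative choice. This stands. The rate is too low only against a tolerability question in which the hold counts.
- **Late holds.** One might add that a hold starting on Day 15 or later cannot exceed 14 days inside the window. The DLT text also covers a delay, which may include a hold running into Cycle 2, so the documents do not settle this and the point does not rely on it.
- **The RP2D looks safe from this.** The MTD was declared on 2 DLTs among 6 evaluable patients in Cohort 7 at 400 mg, where 6 were enrolled, so nobody was replaced there. The Safety Review Committee also weighed wider safety and PK data. Escalation ended in November 2018, while the amendment history dates the proteinuria language to May 2018 and September 2019, so the holds cited may not have applied to every escalation patient. All of this stands.
- **Treated-patient data are already planned.** SAP 10 gives exclusion reasons by dose level; SAP 15 gives Cycle 1 exposure, interruption reasons and a listing of dose intensity in the DLT window; SAP 17.1.3 tabulates adverse events leading to interruption. This is real mitigation, but none of these outputs requires the under-dosing reason to be split by toxicity, or shows DLT incidence with these patients retained.

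**Conclusion.** The gap exists on the text of both documents and the SAP does not close it. A patient with a drug-related hold costing 8 to 14 full Cycle 1 doses, and no event meeting a DLT criterion, leaves the primary-endpoint denominator because the dose was not tolerated.

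At assumed p = 20% and q = 10%, the reported rate is 22.2%, against 30% if such patients count as not tolerating the dose (chance of clearing the level 66.0% against 49.4%), and slightly too high against 20% if they are kept as evaluable without a DLT. These sizes rest entirely on the assumed p and q; if no patient was excluded this way, the effect is zero.

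A reader might infer that the 300 mg MTD/RP2D is biased. The documents do not support that. Cohort 7 is unaffected, and no exclusion is documented. The 300 mg level (n=9) and the initial 400 mg cohorts (n=7) are larger than the 3 to 6 patients in Protocol Table 3, but the reason is not given; replacement is only one possible explanation. Protocol 5.1.1 also speaks of 35 evaluable patients, which neither proves nor excludes replacements. The point concerns what the report will show.

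**What to change.** Leave the DLT definition, the DLT set, the cohort decisions and the MTD rule unchanged.

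1. In SAP 6.3 and 17.1.6, add one supplementary table by dose level. Its denominator is the DLT set plus treated escalation patients excluded because a drug-related adverse event took them below 75% of the Cycle 1 dose. Show (a) protocol-defined DLTs and (b) DLT or toxicity-related Cycle 1 under-dosing. Label it a tolerability sensitivity summary, not a DLT rate.
2. In the same table, give the number of treated patients excluded for other reasons.
3. In SAP 10, split the exclusion reason of less than 75% of dose into toxicity and non-toxicity.
4. Cite the table beside the MTD/RP2D statement in the report.

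The sponsor should also reconcile the 75% and 14-day passages; no threshold is proposed here.

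The cost is SAP wording, one table, and attribution of missed doses from fields the SAP already uses (interruption reasons in SAP 15, action taken in SAP 17.1.3). Escalation is complete, so no dose decision changes. The downside is that the figure shown for a dose level may look less favourable.

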5.1.1.3 Definition of a Dose-Limiting Toxicity (DLT)

All AEs, including DLTs, are to be graded according to the NCI CTCAE, v. 4.03. A DLT is defined as one of the following toxicities occurring during the DLT assessment window (Cycle 1, Days 1-28) and determined by the investigator to have a reasonable possibility of being related to surufatinib.

- Any Grade 4 non-hematological toxicity;
- Any Grade 3 non-hematological toxicity except for nausea/vomiting, diarrhea, constipation, electrolyte imbalances, or transient hypertension downgraded within 3 days with appropriate supportive treatment;
- Grade 4 neutropenia lasting >7 days;
- Grade 3 febrile neutropenia (absolute neutrophil count $<1.0 \times 10^9/L$ with a single temperature of $>38.3^{\circ}\text{C}$ or a sustained temperature of $\geq 38^{\circ}\text{C}$ for more than one hour);
- Grade 4 thrombocytopenia or \geq Grade 3 thrombocytopenia associated with tendency to bleed;
- Dose interruption or delay for >14 days due to toxicity;
- Any life-threatening complication or abnormality not covered in the NCI CTCAE v. 4.03.

In the absence of clinical abnormality, repeat laboratory testing will be conducted to confirm significant laboratory findings prior to designation as a DLT.

5.1.1.4 Definition of Maximum Tolerated Dose (MTD)

The MTD is defined as the maximum dose at which no more than 1 out of 6 patients in a single dose group experiences a DLT in Cycle 1 (Days 1-28).

5.1.2 Dose Expansion Phase

The expansion phase will evaluate the anti-cancer activity of surufatinib, and confirm the safety and tolerability of surufatinib at the RP2D determined at the end of the dose escalation phase.

Under amendment 7 of this protocol, the MTD was declared when 2 of the 6 DLT evaluable patients in Cohort 7 (400 mg QD dose) of the dose escalation phase reported DLTs. There was an ad hoc meeting of the SRC on 30 November 2018. The SRC agreed with the declaration of 300 mg QD as the MTD of surufatinib in this trial and agreed that 300 mg QD is the RP2D going forward. The minutes of this ad hoc SRC meeting were distributed to all investigative sites on the same day. It was also agreed that patients who were already receiving 400 mg QD could remain on this dose, provided that 1) there was no major toxicity and 2) the affected patients gave informed consent not to reduce the dose to 300 mg after discussion with the investigator. However, no patients could have their dose escalated to 400 mg going forward, including all patients in the dose expansion phase.

The safety of all enrolled patients will be closely monitored from the time of the initial dose of investigational treatment until 30 days after the last treatment dose. Any SAEs that occur after the informed consent form (ICF) is signed, but before the first dose of study drug is taken, should also be reported. All AEs will be graded in accordance with the NCI CTCAE v. 4.03. Tumor assessments will be conducted according to RECIST Version 1.1 criteria at screening, Cycle 2 Day 1 and every 8 (± 1) weeks thereafter. Confirmation of

CR and PR is required at no less than 4-week intervals between the date of initial response/progression and the confirmation assessment date.

5.2 Sample Size

Approximately 95 to 150 patients will be enrolled in this two-phase study: 35 patients in the dose escalation phase and approximately 115 additional patients in the dose expansion phase. The actual enrollment number may vary, depending on the number of dose levels evaluated and the number of DLTs observed in each cohort, as well as the potential need to further characterize individual cohorts in the dose expansion phase.

As of Amendment 7, an additional 15 patients will be enrolled into Arm A (BTC) of the Expansion phase, for a total enrollment of at least 30 advanced BTC patients. The reason for increasing enrollment into Arm A (advanced BTC) is that preliminary data from the ongoing patients in this cohort have shown encouraging results. The additional patients will allow further characterization of the safety and efficacy of surufatinib in this patient population. Arm B (pNET) and Arm C (epNET) will enroll at least 15 patients each. If needed, Arm B and Arm C could enroll additional patients in order to characterize further the safety and efficacy of surufatinib in these patient populations.

As of Amendment 8, approximately 45 additional patients with STS will be enrolled to Arm D.

As of Amendment 10, an additional 10 patients will be added to the arm D (STS) for a total enrollment of 55 patients.

5.3 Investigational Site

The study plans to enroll patients at approximately 8 to 15 sites.

5.4 Safety Review Committee

Safety monitoring and evaluation for dose escalation will be carried out by the Safety Review Committee (SRC) upon completion of the DLT observation period of each cohort in dose escalation. The SRC is chaired by the Sponsor's Clinical Program Leader of the surufatinib program, and members will include the principal investigators (PIs), the Sponsor's PK scientist, medical monitor, safety scientist, and the contract research organization's (CRO's) medical monitor. Dose escalation decisions are based on safety and PK data from this ongoing trial, as well as consideration of safety and PK data at comparable drug exposures from patients in previously conducted clinical trials in China.

For the dose expansion phase of the trial, a separate, specific SRC will be established to ensure the safety of all patients treated with study drug in the STS cohort (STS-SCR). Review of available safety laboratories, adverse events, and any other pertinent data available will be reviewed after the first 4 patients in each sarcoma cohort have completed at least 1 cycle of treatment. The recommendations of the STS-SRC will be based on the members' clinical assessment of the cumulative safety data provided for review. The SRC will not be charged with the application of formal statistical stopping rules for safety.

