10.1 Determination of Sample Size

The total number of patients enrolled will depend on the number of dose escalations and the need to further characterize individual cohorts in the expansion phase.

The planned enrollment for this study is approximately 95 to 150 patients, including 35 patients in the dose escalation phase, and approximately 115 patients for the dose expansion phase. Dose expansion phase will enroll patients in specific disease cohorts, 30 patients in the BTC Arm, at least 15 patients each in the pNET and epNET arms, and 55 patients in the STS arm (10 patients with LMS, 10 patients with UPS, 10 patients with epithelioid sarcoma, 10 patients with angiosarcoma, 10 patients with SS, and 5 patients with PVNS).

Sample size for Arm A: BTC cohort in dose expansion phase:

The PFS rate at 16 weeks was selected as the primary endpoint for the expansion phase of the study in patients with BTC. The PFS rate at 16 weeks is defined as the percent of patients without evidence of disease progression or death after 16 weeks on study among the PFS-evaluable patients.

For a BTC cohort with at least 30 evaluable patients, the treatment effect may be considered positive if there are at least 9 evaluable patients without evidence of progression or death after 16 weeks on study. This event will occur with probabilities 90.6% (true positive

rate) if the true PFS rate at 16 weeks is 40%, and 2.8% (false positive rate) if the true PFS rate at 16 weeks is 15%.

In addition, for a cohort with 30 evaluable patients, if 9 (30.0%) patients, or 10 (33.3%) patients without progression or death at 16 weeks are observed, then the lower limit of the 80% two-sided CIs for PFS rate at 16 weeks would be 19.0% and 21.8%, respectively.

Sample size for Arm B: pNET cohort in dose expansion phase:

For a pNET cohort with at least 15 evaluable patients, the treatment effect may be considered positive if there are at least 6 evaluable patients without evidence of disease progression or death after 11 months on study. This event will occur with probabilities 84.9% (true positive rate) if the true PFS rate at 11 months is 50%, and 4.9% (false positive rate) if the true PFS rate at 11 months is 19%.

In addition, for a cohort with 15 evaluable patients, if the 6 (40%) patients or 7 (47%) patients without progression or death at 11 months are observed, the lower limit of the 80% two-sided CIs for PFS rate at 11 months would be 22.6% and 28.2%, respectively.

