Sample size for Arm C: epNET cohort in dose expansion phase:

For a pNET cohort with at least 15 evaluable patients, the treatment effect may be considered positive if there are at least 6 evaluable patients without evidence of disease progression or death after 11 months on study. This event will occur with probabilities 84.9% (true positive rate) if the true PFS rate at 11 months is 50%, and 4.9% (false positive rate) if the true PFS rate at 11 months is 19%.

In addition, for a cohort with 15 evaluable patients, if the 6 (40%) patients or 7 (47%) patients without progression or death at 11 months are observed, the lower limit of the 80% two-sided CIs for PFS rate at 11 months would be 22.6% and 28.2%, respectively.

Sample size for Arm D: STS cohort in dose expansion phase:

Arm D will consist of 6 cohorts of STS subtypes. The LMS, UPS, epitheloid sarcoma, angiosarcoma, and SS cohorts will enroll at least 10 evaluable patients each. The treatment effect may be considered positive if there are at least 3 evaluable patients in each cohort without evidence of disease progression or death after 4 months on study. This event will occur with probabilities of 83.3% (true positive rate) if the true PFS rate at 4 months is 40%, and 7% (false positive rate) if the true PFS rate at 4 months is 10%.

For the PVNS cohort, it is planned to enroll 5 evaluable patients. This sample size is based on feasibility.

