12 OVERSIGHT

12.1 Independent Monitoring

No independent data monitoring is planned for this study. The sponsor will review study safety data on an annual basis, or more frequently, if safety concerns arise.

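### The one scheduled expansion-phase committee review waits for 4 patients per sarcoma cohort to complete a cycle, so patients lost to toxicity or death in Cycle 1 delay it and, if PVNS stops at 5 treated, can leave it untriggered there

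*Protocol*

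**What the plan says.** Protocol 5.4 sets up a Safety Review Committee for the sarcoma arm alone (STS-SRC), with a remit covering every patient given study drug in that arm. It names one review point: the available safety data "will be reviewed after the first 4 patients in each sarcoma cohort have completed at least 1 cycle of treatment". The synopsis and SAP 5.1 repeat it. Section 5.4 gives no calendar date, no count of treated patients, no event-based trigger and no recurring meeting. It also states no pause in enrolment before the review.

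A sarcoma cohort here is a histological subtype: "Arm D will consist of 6 cohorts of STS subtypes" (Protocol 10.1). Five of them are planned at 10 or more: "The LMS, UPS, epitheloid sarcoma, angiosarcoma, and SS cohorts will enroll at least 10 evaluable patients each". The sixth is smaller: "For the PVNS cohort, it is planned to enroll 5 evaluable patients". A cycle is 28 days (synopsis).

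The dose escalation phase counts patients differently. Under Protocol 5.1.1.2 a patient is evaluable by completing Cycle 1 under stated conditions or, alternatively, if the patient "Has a confirmed DLT during the first 28-day treatment cycle".

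Outside the committee, Protocol 12.1 plans no independent data monitoring and adds: "The sponsor will review study safety data on an annual basis, or more frequently, if safety concerns arise".

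**The concern.** Completing a cycle is itself partly a safety outcome. Protocol 5.6 lists intolerable toxicity as a reason for early discontinuation, and death ends treatment. A patient lost either way in Cycle 1 adds nothing to the count of 4. The scheduled review therefore comes later when early tolerability is worse, which is when the committee is most useful. The escalation rule avoids this by letting a DLT stand in for completion; the expansion trigger has no equivalent.

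At stake is the timing of a committee look at aggregate data while further patients may be dosed. In the smallest cohort it may also be whether that cohort's own scheduled look takes place.

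**Working it through.** **The plan's own figures.** The documents attach no probability or timing to this trigger. The Arm D figures around it reproduce: 5 × 10 + 5 = 55 patients, and the rule of at least 3 of 10 gives 83.3% at a true rate of 40% and 7.0% at 10%, as printed in Protocol 10.1.

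**Inputs.** Four completers are required (Protocol 5.4). PVNS is planned at 5 and the other cohorts at 10 (Protocol 10.1). Let q be the chance that a treated patient does not complete Cycle 1. The documents do not give q, so 5%, 10% and 20% are assumptions. Patients are taken as independent with a common q.

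**Formulas.**
- Mean number treated to reach 4 completers: 4/(1 − q).
- Chance that fewer than 4 of n treated patients complete: 1 − P(X ≥ 4), with X ~ Binomial(n, 1 − q). For n = 5 this is 1 − [(1 − q)^5 + 5q(1 − q)^4].

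**Example, q = 10%, n = 5.** 0.9^5 = 0.59049 and 5 × 0.1 × 0.9^4 = 0.32805. The sum is 0.91854, so the chance of no trigger is 0.0815 (8.1%). In counts, 5 treated less 2 lost leaves 3 completers, one short.

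| Assumed q | Mean treated to 4 completers | No trigger, 5 treated | No trigger, 6 treated | No trigger, 10 treated |
|---|---|---|---|---|
| 5% | 4.2 | 2.3% | 0.2% | below 0.001% |
| 10% | 4.4 | 8.1% | 1.6% | about 0.001% |
| 20% | 5.0 | 26.3% | 9.9% | 0.09% |

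The means leave out patients enrolled while the fourth completer finishes the cycle, so the number actually dosed by then may be higher.

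**Reading of the trigger.** The table takes the milder reading, that any 4 completers suffice. If the phrase means the first 4 enrolled and all of them must complete, one loss among them blocks the trigger in any cohort, with chance 1 − (1 − q)^4: 18.5%, 34.4% and 59.0%. The conclusion does not rest on that reading, but the wording leaves it open.

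**The case against.** Three stronger readings are tempting, and the documents support none of them.

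*That toxicity could go unseen until an annual review.* Protocol 12.1 allows sponsor review more often than yearly if concerns arise. SAEs go to the sponsor within 24 hours, and fatal or life-threatening events attributed to the drug are telephoned to the Medical Monitor at once (9.18.1). The sponsor may stop the study on the incidence or severity of adverse events (5.7). These routes respond faster as toxicity worsens. Nothing in 5.4 forbids an extra meeting, and 5.1.2 records an ad hoc SRC meeting, prompted by escalation DLTs, whose decision also bound expansion patients. What remains is that no other committee review is scheduled for the expansion phase.

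*That the PVNS review would never happen after two losses.* This needs enrolment to stop at 5 treated patients. Protocol 10.1 lists "10 patients with SS, and 5 patients with PVNS" but elsewhere speaks of 5 evaluable patients, and 5.2 lets enrolment vary. Against that, no replacement rule is stated for expansion, and evaluability is not tied to completing Cycle 1. An early death is a PFS event, so that patient would probably count as evaluable and not be replaced. The claim holds only with the condition attached.

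*That a large failure rate can be read from the safety database.* The 15.8% in Protocol 2.3 is discontinuation for adverse events over all treatment in a pooled monotherapy population, not a 28-day rate. A q of 30% would give 47.2% for PVNS, but nothing in the documents supports a loss that high. Eligibility requires ECOG 0 or 1 and expected survival above 12 weeks (6.1), which points toward lower values.

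It is also fair to say that wanting four patients with a full cycle of exposure is a legitimate aim, and that the 3+3 evaluability rule serves a different decision. Neither point explains why early losses should postpone the meeting. Finally, 5.4 already bases recommendations on cumulative safety data, so dropouts' data would be seen once a meeting occurs, and meetings triggered by other subtypes can consider PVNS patients.

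**Conclusion.** The point holds in limited form. The scheduled STS-SRC review is conditioned on tolerating a cycle, so early losses postpone it. In the cohorts of 10 this amounts to about 0.2 to 1 extra patient treated on average at q of 5% to 20%, and failure to trigger is negligible. The material case is PVNS, 5 of the 55 planned sarcoma patients. There, non-triggering has a chance of 2.3% to 26.3% if enrolment stops at 5 treated, and 0.2% to 9.9% with a sixth. These figures rest on assumed loss rates, independence between patients, and the reading that any 4 completers suffice. The direction of the effect depends on none of them. This is a modest weakness in scheduled oversight, with partial backstops, that is cheap to remove.

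**What to change.** In Protocol 5.4, the synopsis and SAP 5.1, reword the trigger so that the review takes place once each of the first 4 treated patients in a sarcoma cohort has completed Cycle 1, or has discontinued study drug or died before completing it. The trigger is then met whenever 4 patients are treated, for any loss rate, and never later than under the present wording. It also settles which 4 patients are meant.

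The cost is one sentence in three places, with the same committee and the same data. Some meetings will see slightly less exposure per patient. No change is needed on cumulative data, which 5.4 already provides for.
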